**Statistical Analysis Plan**  
 Sponsor: Selecta Biosciences  
 Protocol No.: SEL-212/302

---

A second estimand for this key secondary endpoint will be defined similarly to the main estimand but with using the while-on-treatment strategy for all intercurrent events (as listed in 6.1 for the primary estimand).

The main and second estimands will be repeated five times, once with the population changed to each of the three defined mITT populations, once with the population changed to the all randomized set, and once with the population changed to the PP set.

These analyses will be repeated for each background medication subgroup: i) no NSAIDs of colchicine, ii) NSAIDs no colchicine, and iii) colchicine.

**6.2.9. Estimands for 'Gout Flare Incidence during Treatment Periods 1-3'**

The main estimand for the key secondary efficacy endpoint 'gout flare incidence in TP1 to 3' is defined as follows:

- Population: Of all patients with gout refractory to conventional treatment defined by the study inclusion / exclusion criteria, the analysis population will include patients who were randomized to study treatment and who were dosed (ITT population).
- Variable: Incidence of gout flare during the whole treatment period from start of treatment until end of month 3. Gout flare incidence is defined as the total number of gout flares a patient experiences in respective time period divided by the length of observation of the patient in this time period.
- Population-level summary: Difference in the incidence of gout flares between each SEL-212 treatment group versus placebo for the whole treatment period (start of treatment until end of Treatment Period 3).
- Intercurrent events:
  - o All intercurrent events (as listed in 6.1 for the primary estimand) except deaths will be considered using the treatment policy strategy
  - o For deaths the while-on-treatment strategy will be used

A second estimand for this key secondary endpoint will be defined similarly to the main estimand but with using the while-on-treatment strategy for all intercurrent events (as listed in 6.1 for the primary estimand).

The main and second estimands will be repeated five times, once with the population changed to each of the three defined mITT populations, once with the population changed to the all randomized set, and once with the population changed to the PP set.

These analyses will be repeated for each background medication subgroup: i) no NSAIDs of colchicine, ii) NSAIDs no colchicine, and iii) colchicine.

This document is confidential.

## 7. General Aspects for Statistical Analysis

### 7.1. General Methods

SAS® version 9.4 or higher will be used for all statistical analyses and tabulations.

In general, summaries will present data by treatment group and overall for each scheduled assessment time where appropriate.

Unless stated otherwise, descriptive summaries will include n, mean, standard deviation, median, minimum and maximum for continuous variables, and n and percent for categorical variables. If there are multiple assessments collected for the same scheduled time the first assessment post-baseline will be used. The last available assessment before start of study treatment will be used as baseline.

Adverse events and medical history will be coded according to the most recent version of Medical Dictionary for Regulatory Activities (MedDRA). Prior and concomitant medications will be coded using the most recent WHO Drug Dictionary version. The actual version of MedDRA and WHO drug used will be noted in the footnote of the respective output.

### 7.2. Key Definitions

Baseline is defined as the last non-missing value prior to the start date and time of the study drug. For Health questionnaires (including HAQ-DI, SF-36, and PGA), gout flare assessment, tender joint assessment and swollen joint assessment, if no assessment is available prior to the start time of the study drug, assessments post the start of study drug but on the date of first study drug administration may be considered as Baseline. Tophus status at baseline in the study will be based on IRT.

Day 0 of Treatment Period 1 is defined as the first date of study drug administration.

Overall study day will be calculated as date of event/collection – first dose date of the study.

Study day within each treatment period will be calculated as date of event/collection – first dose date at each treatment period to be consistent with protocol which defines the day of dosing in each treatment period as day 0.

### 7.3. Missing Data

Missing data will be imputed for the primary efficacy and key secondary efficacy variables as described in Section 9.

Missing or incomplete dates in safety data: In all listings, missing or incomplete dates will be left as they have been recorded. However, for calculation and sorting based on dates and for consideration in summary tables, the following method will be used: The most conservative approach will be systematically considered (i.e. if the onset date of an AE/concomitant medication is missing or incomplete, it is assumed to have occurred during the study treatment phase (i.e. a TEAE for AEs) except if the partial onset date indicates differently). A missing/incomplete date of medical history or disease diagnosis will be assumed to have occurred before any study treatment.

Missing TEAE relationship will be imputed by 'related' for tabulation.

This document is confidential.

**Statistical Analysis Plan**  
Sponsor: Selecta Biosciences  
Protocol No.: SEL-212/302

---

#### **7.4. Unscheduled visits**

Unscheduled visit measurements will be included in analyses and treatment summaries in the following circumstances:

- i) If there are missing data at a scheduled visit, but data available at an unscheduled visit that occurred after the previous scheduled visit, and prior to the next scheduled visit.
  - a. In the event there are more than one unscheduled visit between the previous scheduled visit and the next scheduled visit, the closest measurement to the missed target day will be used.
  - b. If there are multiple records within the same distance from the target day, the latest record will be used.
- ii) Derivations of baseline/last-on-treatment measurements.
- iii) For all safety parameters, if there are multiple measurements within a visit window, then the record closest to the target day will be used.
  - a. In the event there are more than one unscheduled visit between the previous scheduled visit and the next scheduled visit, the closest measurement to the missed target day will be used.
  - b. If there are multiple records within the same distance from the target day, the latest record will be used.

Otherwise, data collected at unscheduled visits will be included in the data listings but will not be included in the analyses or in treatment summaries.

This document is confidential.

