#### **10.4. Laboratory Evaluations**

Laboratory data will be presented in separate tables for each laboratory test type (hematology, blood chemistry, coagulation, antibodies, lipids). Each laboratory parameter will be summarized by scheduled visit and by treatment group, overall SEL-212 and total, presenting actual values and change from baseline. The values from unscheduled visits will be included in analyses according to the rules set out in Section 7.4. Shift tables of the number and percentage of patients below normal range (low), within normal range (normal) and above normal range (high) at each scheduled post-baseline visit compared to the low/normal/high categorization at baseline will be provided by treatment group. A listing of clinically significant abnormal values will be provided in the tables section. Biomarkers and genetic markers will also be summarized by treatment group. Pregnancy test results and drug screen results will be listed only.

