**10.6. ECG**

For each 12-lead ECG variable the actual value and the change from baseline will be summarized for the scheduled visits by treatment group, overall SEL-212 and total.

A shift table of the number and percentage of patients with normal and abnormal, and clinically significant abnormal values at each scheduled post-baseline visit compared to the normal / abnormal /clinically significant abnormal categorization at baseline will be provided by treatment group for the overall interpretation. A frequency table with number and percentage of patients with abnormal clinically significant overall interpretation will be presented for each scheduled visit by treatment group, overall SEL-212 and total. Additionally, a frequency table with number and percentage of patients with noteworthy QTcF/QTcB values ( $> 450$ ,  $> 480$  and  $> 500$  ms) during the study and of patients noteworthy QTcF/QTcB changes from baseline ( $\geq 30$  but  $< 60$ ;  $\geq 60$  ms) will be provided by treatment group, overall SEL-212 and total.

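### The QTc outlier table in SAP 10.6 is labelled as covering the study, but SAP 7.4 leaves out unscheduled ECGs that fall outside three exceptions

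*SAP*

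**What the plan says.** SAP 7.4 lists three circumstances in which an unscheduled measurement enters analyses and summaries:

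- (i) The scheduled value is absent: "If there are missing data at a scheduled visit, but data available at an unscheduled visit that occurred after the previous scheduled visit". The unscheduled visit must also precede the next scheduled one. If there are several, the closest to the missed target day is taken.
- (ii) The value is needed to derive baseline or the last measurement on treatment.
- (iii) A rule for safety data: "For all safety parameters, if there are multiple measurements within a visit window, then the record closest to the target day will be used". Ties go to the latest record.

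The closing sentence of 7.4 begins with the word Otherwise and covers what is left: "data collected at unscheduled visits will be included in the data listings but will not be included in the analyses or in treatment summaries".

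SAP 10.6 plans, by treatment group, "a frequency table with number and percentage of patients with noteworthy QTcF/QTcB values" above 450, 480 and 500 ms, gives the period as during the study, and adds categories for change from baseline (30 to below 60 ms, and 60 ms or more). It makes no exception to 7.4. Protocol 13.5.5 has the same thresholds but names no period.

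For laboratory data, SAP 10.4 says: "The values from unscheduled visits will be included in analyses according to the rules set out in Section 7.4". Its shift tables show categories "at each scheduled post-baseline visit compared to the low/normal/high categorization at baseline will be provided by treatment group".

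SAP 7.1 has a general rule for repeats: "If there are multiple assessments collected for the same scheduled time the first assessment post-baseline will be used".

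**The concern.** The three exceptions choose a record because the scheduled one is missing, because of its place in the sequence, or because it lies near the target day. None chooses by severity. An ECG taken between visits is likely to have been prompted by a symptom or an earlier result, and it is the kind of record that a whole-study outlier count is meant to catch.

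With a single scheduled post-baseline ECG in a completer, the QTc table depends heavily on how unscheduled ECGs are treated. If 7.4 is applied as written, the table describes one time point under a label that promises the whole treatment phase. If a programmer instead follows the label in 10.6, the table will include records that 7.4 excludes. Two competent programmers could therefore produce different counts from the same data.

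**Working it through.** The plan states no figure on this point, so there is nothing to reproduce. The check is a trace through the rules, followed by a count of days.

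**Inputs**

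- ECG schedule (Protocol Appendix A; SAP Table A): Screening, one visit late in Treatment Period 6, and Early Termination. The table layout available to me does not settle whether the Treatment Period 6 ECG is at Day 21 or Day 28, so both are shown.
- Safety laboratory schedule after baseline (Protocol 7.1.2): Day 21 of each of the six periods plus Day 28 of Treatment Period 6, which is 6 + 1 = 7 draws in a completer.
- Visit windows (SAP Table A, note 2): Day 21, +2/-1 days, which is 4 days; Treatment Period 6 Day 28, +3/-4 days, of which Days 24 to 28 (5 days) lie inside the treatment phase.
- Treatment phase: 168 days. Planned arm size: about 47.
- Assumption: a visit window in 7.4 (iii) is the protocol visit window, because the SAP defines no separate analysis windows.

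**Trace of one hypothetical patient.** QTcF is 510 ms on an unscheduled ECG in Treatment Period 3 and normal on the scheduled ECG in Treatment Period 6.

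1. Exception (i): the scheduled ECG is present, so it does not apply.
2. Exception (ii): the value is neither baseline nor the last on treatment, and 10.6 has no last-on-treatment summary.
3. Exception (iii): Treatment Period 3 contains no ECG visit window, so it does not apply.
4. The closing clause applies, and the value goes to listings only.

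Under 7.4 the patient is counted in none of the three threshold categories. Under the plain words of 10.6 the patient is counted in all three.

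**Days on which exception (iii) could admit an unscheduled value**

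- ECG at Day 28: 5/168 = 3.0%. ECG at Day 21: 4/168 = 2.4%.
- Laboratory: 6 × 4 + 5 = 29 days; 29/168 = 17.3%, leaving 139/168 = 82.7% outside any window.

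Even inside the window, the record closest to the target day is used, not the most extreme.

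**Size.** One such patient is 1/47 = 2.1 percentage points in an arm. This shows the weight of one patient; it is not an expected rate.

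**Repeat values.** Take two results from the same Day 21 visit. SAP 7.1 uses the first. Under 7.4 (iii) both are equally far from the target day, so the latest is used. The two rules give opposite choices, and neither is given precedence.

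**The case against.** A reader might infer that 7.4 keeps unscheduled results out of all summaries. It does not: the excluding sentence is a residual clause after three exceptions, one written for safety parameters, and SAP 10.4 repeats that unscheduled laboratory values enter under those rules.

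A reader might also infer that every QTc outlier in Treatment Periods 1 to 5 goes uncounted. The documents do not support that. An Early Termination ECG can fall in those periods, and exception (i) can admit an unscheduled ECG when the Treatment Period 6 ECG is missing, although only the one closest to the target day.

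Nor are the laboratory shift tables wrong. Protocol 13.5.3 and SAP 10.4 both define them by scheduled visit, and seven post-baseline draws are not few. The infusion-reaction samples in Protocol 10.7 are taken around dosing, outside the Day 21 windows, but by-visit tables do not claim to hold them.

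There are also other routes into the report. Clinically significant laboratory and ECG abnormalities are reported as adverse events (Protocol 12.2.2.6). Leukopenia, hyperlipidemia, proteinuria and worsening renal function are events of special interest if judged clinically significant, with rate differences and 95% confidence intervals when they occur in at least 2% of patients (SAP 10.3). Unscheduled assessments are flagged in listings (SAP 10). These routes are real, and no claim that safety is understated by a given amount can be made. They rest on investigator judgement, however. QTc is not an event of special interest, and none of them counts threshold crossings by arm.

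The number of unscheduled ECGs is unknown. The infusion-reaction kit contains blood tests only, and Protocol 12.1.4 refers only to the schedule. Few such ECGs may exist.

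Finally, an any-time count mixes testing frequency with drug effect if the arms are tested unequally. A footnote discloses this but does not remove it.

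On the repeat rule, 7.4 (iii) is the more specific and would naturally govern safety data. That is a fair reading, but the SAP does not state it.

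**Conclusion.** The point holds for the QTc category tables. When the scheduled post-baseline ECG is present, an outlier on an unscheduled ECG outside its visit window is not counted, so the table does not deliver what its label in 10.6 says. The effect is 2.1 percentage points of a planned arm for each such patient, and the number of patients cannot be estimated from the documents. The table is descriptive, and no confirmatory test is affected.

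This rests on three readings: that 7.4 governs 10.6, which has no exception of its own; that a completer has one scheduled post-baseline ECG; and that visit windows are those of the protocol.

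For the laboratory shift tables there is no error, only room for an optional addition. The overlap between 7.1 and 7.4 is a minor clarification.

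**What to change.** - In SAP 7.4 and 10.6, state that the QTc threshold and change-from-baseline category tables use all post-baseline ECGs, scheduled or unscheduled. Footnote the number of ECGs per arm, because testing frequency may differ. Keep scheduled values, under the existing 7.4 rules, for by-visit summaries.
- Optionally, add a worst-post-baseline row to the laboratory shift tables in SAP 10.4.
- State that 7.4 (iii), not the first-assessment rule in 7.1, governs repeat safety values.

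If the sponsor prefers to keep the present data rule, the minimum is to relabel the QTc table so that its restriction to scheduled ECGs and the 7.4 exceptions is plain.

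The cost is a few SAP lines and some programming. No new data are needed. The remaining downside is that patients tested more often have more chances to show an outlier; the footnote lets the reader judge this but does not correct for it.

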## 8. Demographic, Other Baseline Characteristics and Medication

### 8.1. Patient Disposition and Withdrawals

Patient disposition data will be listed. Summary tables reflecting the number of patients for the following will be presented:

- Screened (or enrolled) patients
- ITT, SS, mITT, all randomized, and PP patients
- Patients who complete the study treatment
- Patients who early terminate study treatment overall and by treatment period together with reasons
- Patients who complete the study
- Patients who early terminate the study overall and by treatment period together with reasons

Screen Failure subjects will be listed with reason for failure.

A figure of the percentage of patients who discontinued the study treatment will be presented by treatment and period. Additionally, a figure of the percentage of patients who discontinued the study treatment because of the stopping rule will be presented by treatment and period.

### 8.2. Demographic and Other Baseline Characteristics

Demographic characteristics such as gender, age, race, ethnicity, height, weight, BMI, time since first gout diagnosis and estimated glomerular filtration rate (eGFR) will be summarized for the ITT and the SS population, by treatment and overall. Demographic characteristics will be listed for all randomized patients.

Age (years) will be calculated based on date of signed informed consent as:

(Date of informed consent - date of birth) / 365.25 and truncated to complete years.

BMI ( $\text{kg}/\text{m}^2$ ) will be calculated as: Weight (kg)/[Height(cm)/100].

### 8.3. Medical History

Medical history will be coded using current version of Medical Dictionary for Regulatory Activities (MedDRA®). Medical history will be listed for all randomized patients. No summaries will be provided.

### 8.4. Other Baseline Characteristics

Tophus assessment at screening, gout flare assessment at screening and baseline and the number of tender and swollen joints at baseline will be summarized by treatment group, overall SEL-212 and total. In addition, sUA at screening and baseline (Day 0 pre-dose) will be summarized by treatment group, as well as the change in sUA from screening to baseline.

### 8.5. Medication

Prior medication is defined as any medication which has an end date prior to the date of first dose of study drug administration.

This document is confidential.

**Statistical Analysis Plan**  
Sponsor: Selecta Biosciences  
Protocol No.: SEL-212/302

---

Concomitant medication is defined as any medication which has an end date or is continuing after the date of first dose of study drug administration or has a missing end date.

The original verbatim terms collected in the eCRF for prior and concomitant medications will be coded using the World Health Organization Drug Dictionary (WHO-DD current version).

Listings will include the therapeutic (i.e., the second level of Anatomical Therapeutic Chemical [ATC] classification system code, that is, corresponding to the first 3 figures), preferred name (the fourth level of the ATC code, that is, corresponding to the first 5 figures) and verbatim text. The listings will be sorted by treatment group, patient id, chronological start date, stop date, therapeutic class, preferred name and verbatim name and will contain all randomized patients.

A frequency table of the number and percentage of patients will be provided for prior medications and concomitant medications by therapeutic class and preferred name for each treatment group and overall on the ITT population.

Premedication for gout flare and premedication against infusion reactions (provided before start of dosing in each treatment period) will be summarized separately by treatment group and period, if applicable.

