Overall, most TEAEs have been mild or moderate in severity. Eight (8) of the 83 (9.6%) subjects who received SEL-212 experienced a total of 14 severe TEAEs. Four (4) subjects experienced a single severe TEAE including anemia, gout, rotator cuff syndrome, and deep vein thrombosis (DVT); 2 subjects experienced 2 severe TEAEs including gastrointestinal haemorrhage and gout; and pulmonary embolism and DVT; and 2 subjects experienced 3 severe TEAEs including: arthralgia, joint swelling, and ligament pain; and presyncope and 2 gout attacks. In addition, 2 subjects who received SEL-212 each experienced a life-threatening TEAE, both anaphylactic reactions.

A total of 6 of the 86 (7.0%) subjects who received KRYSTEXXA experienced a total of 6 severe TEAEs. Subjects experienced a single severe TEAE including: 2 gout, an anaphylactic reaction, drug

hypersensitivity, gastroenteritis, and an infusion-related reaction. In addition, 2 subjects who received KRYSTEXXA each experienced a life-threatening TEAE of cerebrovascular accident and hypertensive emergency, respectively. There have been no concerning trends in laboratory values, vital signs, or physical examination findings (data not shown).

Twelve (12) of the 169 (7.1%) subjects enrolled have experienced a total of 14 SAEs. Six (6) of the 83 (7.2%) subjects who received SEL-212 experienced a total of 7 SAEs and 6 of the 86 (7.0%) subjects who received KRYSTEXXA experienced a total of 7 SAEs. Two (2) of the SEL-212 SAEs were considered related or possibly related to SEL-212 and 3 of the KRYSTEXXA SAEs were considered related or possibly related to KRYSTEXXA by the investigator.

No deaths have been reported during the study.

In summary, the safety profile of SEL-212 in the ongoing Phase 2 clinical trial has not demonstrated any unexpected TEAEs. In the dose ranging Phase 2 Study SEL-212/201, in general, TEAEs were most frequently observed after the first treatment cycle and diminished with successive treatment cycles. Therefore, the potential risk of TEAEs did not appear to increase with repeated exposure to SEL-212.

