If an infusion reaction occurs, Investigators are permitted to use concomitant medications or treatments deemed necessary to provide adequate patient care. Investigators should also utilize the infusion reaction lab kit (samples for: chemistry, hematology, coagulation, histamine, serum tryptase, and anti-uricase) provided in the Study Operations Manual to collect additional blood specimens. In the case of a Grade 3 or 4 infusion reaction occurring during an infusion, the administration of study drug should be immediately discontinued, and the affected patient should be treated according to the clinical trial site's protocol for infusion reactions (e.g., monitoring, administration of antihistamines, corticosteroids, fluids and epinephrine, as clinically indicated). The patient should be withdrawn from subsequent study drug treatment.

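### SAP 8.5 leaves a medication that ends on the date of first dose in neither the prior nor the concomitant class, so it drops out of both frequency tables

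*SAP*

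**What the plan says.** SAP 8.5 gives two definitions. For the first class: "Prior medication is defined as any medication which has an end date prior to the date of first dose of study drug administration". For the second: "Concomitant medication is defined as any medication which has an end date or is continuing after the date of first dose", extended to any medication that "or has a missing end date". SAP 7.2 fixes the date of first dose as Day 0 of Treatment Period 1.

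The definitions feed one planned output: "A frequency table of the number and percentage of patients will be provided for prior medications and concomitant medications by therapeutic class and preferred name". It is broken down by arm, with an overall column, and uses the ITT set. Two kinds of drug are reported apart from it. One is gout-flare premedication. For the other, "premedication against infusion reactions (provided before start of dosing in each treatment period) will be summarized separately by treatment group and period".

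On treatment of infusion reactions, Protocol 10.7 states: "If an infusion reaction occurs, Investigators are permitted to use concomitant medications or treatments deemed necessary to provide adequate patient care". Its examples for a severe reaction are antihistamines, corticosteroids, fluids and epinephrine.

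**The concern.** The two classes are evidently meant to be complementary, but their boundaries do not meet. A drug given once at the site to treat a reaction at the first infusion normally starts and ends on the date of first dose. Applied as written, the SAP puts it in neither table, although the protocol's own term for it is concomitant medication. The identical drug given once at any of infusions 2 to 6 ends after the date of first dose and is counted. The tables therefore treat the first infusion differently from the other five, for no stated reason. At stake is the completeness of a descriptive safety table presented by arm.

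**Working it through.** No figure in the plan bears on this point, so the check is one of logic. Let d be the end date minus the date of first dose, in days.

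- Prior (SAP 8.5): d < 0.
- Concomitant (SAP 8.5), with the words about falling after the first dose governing both the end date and continuation: d > 0, or ongoing, or end date missing.
- Proposed concomitant: d ≥ 0, or ongoing, or end date missing.

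| End date | Prior | Concomitant as written | Concomitant as proposed |
|---|---|---|---|
| d = -10 | yes | no | no |
| d = -1 | yes | no | no |
| d = 0 | no | **no** | yes |
| d = +1 | no | yes | yes |
| d = +10 | no | yes | yes |
| ongoing | no | yes | yes |
| missing | no | yes | yes |

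The only gap is d = 0. Under the proposed rule every case falls in exactly one class.

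**Alternative reading.** If the mention of an end date is taken as unqualified, every drug with any end date is concomitant, including d = -10 and d = -1. All prior medication would then also be concomitant, which cannot be meant. The sentence needs correcting on either reading.

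**Does another rule close the gap?**
- SAP 7.3 handles missing or incomplete dates. A complete end date equal to Day 0 is neither.
- The infusion-reaction premedication summary covers drugs given before dosing starts, not drugs given in response to a reaction.
- SAP 12 lists one departure from the protocol, the use of ANOVA for gout flares. It does not suggest that the exclusion is deliberate.

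**Can such records occur?** Protocol 12.2.1.5 classes a drug-related event within 24 hours of infusion start as an infusion reaction, and keeps patients under observation for about 4.5 hours from the start. Treatment that begins and ends on the dosing date is realistic.

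**Size for one patient and one arm.** The table counts patients per therapeutic class and preferred name. A patient is missed for a row only if no drug in that row is used later. For such a patient the entry goes from 1 to 0. With about 47 patients per group (Protocol synopsis; SAP 3.4), one missed patient changes the row by 1/47 = 0.021, or about 2.1 percentage points. The documents give no rate of first-infusion reactions or of same-day treatment, so the number of missed patients cannot be estimated.

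**The case against.** The strongest reply is that this is a boundary slip of a word or two in a descriptive section, that the intent is plain, and that a programmer would probably use on-or-after anyway. The intent is indeed plain, but the text as written gives the wrong result and should not rely on silent correction.

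The limits on impact also stand. SAP 10.3 tabulates infusion reactions by arm as adverse events, with a hypersensitivity subset and exposure-adjusted rates for events of special interest. None of that uses the 8.5 definitions. The medication listings cover all randomized patients and state no exclusion by class. Later use of a drug in the same row restores the patient's count. That repair is not guaranteed: Protocol 10.7 says that a patient with a Grade 3 or 4 reaction during an infusion should be withdrawn from further study drug, so a patient so withdrawn after the first infusion has no later infusion at which the drug might recur.

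A reader might infer three stronger things, and the documents support none of them.

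- *That this is the one planned tabulation of infusion-reaction treatment.* It is a general table of all medications, with no split by indication, treatment period or linked event. Even with the boundary corrected, rescue use could not be read from it.
- *That first-infusion reactions predominate, so the loss is large.* The Phase 2 sentence that "TEAEs were most frequently observed after the first treatment cycle and diminished with successive treatment cycles" sits in the section on Study SEL-212/202 but describes Study SEL-212/201, and concerns adverse events in general. Protocol 5.5 links reactions to the approved uricase with high antibody titer, and patients here have had no prior uricase. That is indirect evidence, but it does not point to the first infusion.
- *That use is understated mainly in the active arms.* This is plausible, since an infusion reaction is by definition drug-related, but nothing in the documents shows or quantifies it.

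**Conclusion.** The gap is real and follows from the text: an end date equal to the date of first dose satisfies neither definition in SAP 8.5. Same-day treatment of a first-infusion reaction is the clearest example, but any drug stopped on that date is affected. The consequence is confined to the two descriptive medication tables. No efficacy test, adverse-event analysis or stated listing rule changes. The conclusion assumes that the definitions are programmed as written and that at least some patients have a drug ending on Day 0 of Treatment Period 1 with no later use in the same row. How many is unknown. This is a minor correction that is worth making because it costs almost nothing.

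**What to change.** In SAP 8.5, define concomitant medication as *any medication with an end date on or after the date of first dose, or ongoing, or with a missing end date*. Leave the prior definition as it is, and keep protocol premedication in its separate summary.

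The cost is a few words in the SAP and one inequality in the program. The downside is that a few drugs stopped on Day 0 before the infusion will be counted as concomitant. If clock times are collected for medications, those drugs could be classed as prior. The documents do not say that they are: Protocol 12.2.2 asks for times of adverse events while the patient is in the clinic, and states nothing equivalent for medications. The date-based rule should therefore be the default.
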